16.6. DURATION OF RESPONSE (DOR)

Duration of response (DoR): defined as the time from when the first response (CR, CRi, PR, nPR, VGPR, PR-L, and MR) was achieved until the earlier of the first documentation of definitive disease progression or death from any cause, whichever is earlier. If patients do not have disease progression or death, they will be censored following the same rules as for PFS. Only patients with response of CR, CRi, PR, nPR, VGPR, PR-L, or MR will be included in the analysis for DoR.

DoR (months) = (<date of first documentation of definitive PD or death from any cause or censoring > - <date of first response> + 1)/30.4375.

Median and quartiles for DoR, and the DoR rates at 6 months, 12 months, along with the two-sided 95% CI will be estimated and Kaplan-Meier curve will be plotted by dose level in stage 1 and by the malignancy type in stage 2. The 95% CI for the median will be calculated from a log-log transformation based on the method by Brookmeyer and Crowley (1982).

DoR data will be listed for all patients in EAS.

16.7. TIME TO RESPONSE (TTR)

TTR is defined as the time from the first dose of study treatment to the first occurrence of CR, CRi, PR, nPR, VGPR, PR-L, or MR. Only patient with response of CR, Cri, PR, nPR, VGPR, PR-L, or MR will be included in the analysis for TTR.

TTR = (< date of first response> - < date of first dose of study medication> + 1)/30.4375.

TTR will be summarized by descriptive statistics by dose level in stage 1 and by the malignancy type in stage 2.

TTR data will be listed for all patients in EAS.

16.8. TUMOR BURDEN

Tumor burden is defined as the sum of the product of diameters of all target measurable lesions at each tumor assessment visit.

The best percent change from baseline in tumor burden is calculated as:

 (The minimum tumor burden among post-baseline assessments – Baseline tumor burden value)/Baseline tumor burden value × 100

Tumor burden will be missing for that assessment visit if there is a missing value of the product of diameters. Thereof a patient will be considered not evaluable for the measure of the best percent change from baseline in tumor burden for that visit.

Best percent change from baseline in tumor burden will be summarized by descriptive statistics. A waterfall plot of the best percent change from baseline in tumor burden will be presented for EAS, BOR will be labeled in the plot. Patients without any baseline or evaluable post-baseline assessments will be completely excluded from the plots. Patients without any target lesions at baseline will be excluded as well.

Different color will be presented to differentiate various dose levels (for stage 1) and the different type of malignancy in stage 2.

A listing with the tumor assessments at baseline and each tumor assessment visit will be presented, including each component for tumor assessment.

A swimmer plot of duration of treatment will be presented from date of first dose until date of last dose. Treatment reduction and interruption will be shown in the exposure box for each patient. Tumor responses for each tumor assessment will also be labeled in the plot.

17. SAFETY OUTCOMES

All summary results for safety outcomes will be based on the FAS, except DLTs summaries which are based on the DEAS.

Adverse Events (AEs) will be coded using MedDRA version 26.0 or higher. AE and laboratory test results severity will be performed with the National Cancer Institute Common Terminology criteria for adverse events (NCI CTCAE) V5.0.

17.1. Dose Limiting Toxicities (DLTs)

DLT is defined as the occurrence of any of the following treatment emergent adverse events (TEAE) during the DLT assessment window (Cycle 1, Day 1 through Cycle 1, Day 28), unless clearly unrelated to study medication:

Nonhematologic toxicity: All nonhematologic TEAEs of Grade 3 or greater with the

exception of:

- Grade 3 nausea or vomiting that can be controlled by supportive therapy
- b. Hematologic toxicity:
 - Grade 4 neutropenia lasting for more than 5 days
 - Grade 4 thrombocytopenia or Grade 3 thrombocytopenia with bleeding event or requiring platelet transfusion
 - iii. Grade ≥3 febrile neutropenia (defined as ANC <1000/mm3 with a single temperature of >38.3°C [101°F] or a sustained temperature of ≥38°C [100.4°F] for more than 1 hour)
 - Grade 4 anemia not explained by underlying disease
- c. Any TEAE requiring a dose delay of ≥15 days
- d. Any case of Hy's Law (defined as the finding of an elevated ALT or AST in combination with either an elevated total bilirubin (≥2 × ULN)) collected as Adverse Event of Special Interest.

For all patients in Stage 1, DLTs will be assessed during a DLT assessment window of 28 days (i.e. from Cycle 1, Day 1 [the day of first administration of treatment] through Cycle 1, Day 28). DLT is collected in the "Dose-Limiting Toxicity Assessment" CRF page.

DLT will be coded using MedDRA Version 26.0 or higher. The number and percentage of patients with DLTs will be based on the number of patients in the DEAS by SOC, PT and CTCAE grade. SOC/PT will be sorted in descending frequency of the total number of patients, SOC/PT will be presented alphabetically for SOC/PT of the same frequency. By-patient listing of DLTs will be presented with SOC, PT and CTCAE grade in the listing.

17.2. ADVERSE EVENTS

Treatment-emergent adverse events (TEAEs) are defined as AEs with onset date on or after the first dose of study medication and no later than 30 days after the date of last study treatment administration or start of a new treatment of anti-neoplasm therapy, whichever is earlier. An exception is that study medication related SAE collected later than 30 days after the last treatment date or start of a new treatment of anti-neoplasm therapy will be treated as TEAEs.

Refer to Section 7.10 for handling of partial dates for AEs. In the case where it is not possible to classify an AE as treatment-emergent or not, the AE will be classified as treatment-emergent.

All AEs will be listed, and only TEAE will be summarized.

The missing severity will be classified as grade 3. Relationship, as indicated by the Investigator, is classified as "Not related", "Related". TEAEs with a missing relationship to study medication will be regarded as "related" to study medication.

Protocol Number: 2018-689-00US1 Page 37 of 43

TEAE OVERVIEW

An overall summary of TEAEs will include the number of patients with:

- Any TEAE
- Any TEAEs by maximum CTCAE grade
- Any TEAE of CTCAE Grade 3 or higher
- Any TEAE Leading to Dose Modification
 - Any TEAE Leading to Dose Reduction
 - o Any TEAE Leading to Drug Interruption
- Any TEAE Leading to Drug Discontinuation
- Any TEAE Leading to Death
- Any Treatment Related TEAE
- Any Treatment Related TEAE of CTCAE Grade 3 or higher
- Any Treatment Related TEAE Leading to Dose Modification
 - Any Treatment Related TEAE Leading to Dose Reduction
 - Any Treatment Related TEAE Leading to Drug Interruption
- Any Treatment Related TEAE Leading to Drug Discontinuation
- Any Treatment Related TEAE Leading to Death
- Any Serious TEAE
- Any Treatment Related Serious TEAE
- Any Special Interest TEAE (AESI)
- Any Treatment Related AESI

TEAE SUMMARY

All TEAE will be summarized (the number and percent of patients) by SOC, PT and maximum CTCAE grade (All Grade, Grade ≥3, Grade 1/2).

The following categories will be summarized (the number and percent of patients) by PT and maximum CTCAE grade (All Grade, Grade ≥3, Grade 1/2).

	Summary scope
	- Any TEAE
	- TEAEs with CTCAE grade 3 or higher (maximum CTCAE
	grade by Grade 5, Grade 4, Grade 3)
TEAE	- TEAEs leading to dose modification
TEAE	 TEAEs leading to dose interruption
	 TEAEs leading to dose reduction
	- TEAEs leading to discontinuation of study drug
	TEAEs leading to death (by PT only)

	Summary scope
	 Any treatment-related TEAE
Treatment-related	- Treatment-related TEAEs with CTCAE grade 3 or higher
TEAE	(maximum CTCAE grade by Grade 5, Grade 4, Grade 3)
	 Treatment-related TEAEs leading to death (by PT only)
Serious TEAE	- All serious TEAE
Serious TEAE	- Treatment-related serious TEAEs

If a subject experienced the same adverse event (as identified by MedDRA preferred term) more than once during the study, the worst occurrence (e.g. worst grade) will be counted. Similarly, if a subject experienced more than one occurrence of the same SOC/PT, the worst occurrence (e.g. worst grade) will be counted within a particular SOC/PT. When summarizing AE by CTCAE grade, if a subject experienced more than one occurrence of the same SOC/PT, the worst severity grade will be counted. Each summary will be ordered by descending order of incidence of SOC and PT within each SOC. If the frequencies of SOC/PT tie, an alphabetic order of SOC/PT will be applied

- Serious adverse events (SAEs) are those adverse events recorded as "Serious" on the "Adverse Events" page of the (e)CRF.
- AEs leading to study medication reduction will be identified as those AEs with a response of "Dose reduced" to the item "Action taken with the study treatment" in the eCRF page of "Adverse Events".
- AEs leading to study medication interruption will be identified as those records with a response of "Drug interrupted" to the item "Action taken with the study treatment" in the eCRF page of "Adverse Events".
- AEs leading to discontinuation of study medication are those AEs with "Drug permanently discontinued" dose action from the eCRF page of "Adverse Events".
- AEs leading to Death are those events which are recorded as "Fatal" in Outcome question/Serious AE related question or Grade 5 in CTCAE grading system on the "Adverse Events" page of the (e)CRF.

AESI SUMMARY

AEs of special interest (AESI) are listed in the below table, and will be identified by MedDRA Query (SMQ):

AESI Category	Search terms	SMQ Code
Hepatic function	MedDRA SMQ "Drug related	20000006 (exclude:
abnormal	normal hepatic disorders - comprehensive	
	search [exclude tumors]" (narrow)	20000012)

MedDRA SMQ "Infective	20000231
pneumonia" (narrow)	
MedDRA SMQ "Noninfectious	20000218
diarrhoea" (narrow+broad)	
MedDRA SMQ "Interstitial lung	20000042
disease" (narrow)	
MedDRA SMQ "Severe cutaneous	20000020
adverse reaction" (narrow)	
	pneumonia" (narrow) MedDRA SMQ "Noninfectious diarrhoea" (narrow+broad) MedDRA SMQ "Interstitial lung disease" (narrow) MedDRA SMQ "Severe cutaneous

All AESIs will be summarized in frequency and percent by AESI category, PT and maximum CTCAE grade (All Grade, Grade ≥3, Grade 1/2). The followings will also be summarized for each AESI category:

- AESI
- Treatment Related AESI
- AESI of CTCAE Grade 3 or higher
- AESI meeting SAE criteria
- AESI leading to dose modification
- AESI leading to dose reduction
- AESI leading to dose interruption
- AESI leading to dose discontinuation
- AESI leading to death

Moreover, time to AESI onset (days), AESI duration (days) and AESI outcome (the number and percent of patients) will be summarized descriptively.

Time to AESI onset is defined as the time interval from the date of first dose of study drug to the earliest onset date among all AESIs. That is, if a subject has multiple AESI occurrences, the earliest AESI onset date will be used as the onset date to calculate time to onset of AESI.

AESI duration (days) will only be calculated for ended AESI as (AE end date-AE start date+1).

All AE will be listed, including AE term, start date, end date, severity, whether the AE is DLT, change of CTCAE grade, whether the AE is SAE, classification of SAE (if SAE), whether the AE is AESI, relationship to study drug, action taken, outcome will be presented in subject data listings. If the AE is ongoing at the data cut-off date, it will be reported as 'Ongoing' in the listing.

In addition, separate listings of all SAEs, AESIs, AEs leading to death and AEs leading to discontinuation of study drug will be provided.

17.3. **DEATHS**

The information recorded in CRF "Death Details" page will be presented in the listing, and the on-treatment death (defined as death during the date of first dose to 30 days after the last dose of study drug or prior to the start of a new anti-cancer therapy, whichever comes first) will be flagged.

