6.3.1.3 Persistent or Recurrent Adverse Events

A persistent AE is one that extends continuously, without resolution between patient evaluation time points. Such events should only be recorded once in the CRF. The initial severity (intensity or grade) of the event will be recorded at the time the event is first reported. If a persistent adverse event becomes more or less severe, it should also be recorded on the Adverse Event CRF as a new entry.

A recurrent AE is one that occurs and resolves between patient evaluation time points and subsequently recurs. Each recurrence of an adverse event should be recorded as a separate event on an AE/SAE CRF.

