6.3.1.9 Worsening of Lymphoma

Worsening and/or progression of the lymphoma should not be recorded as an AE or SAE, unless the progression directly leads to the patient’s death, then the disease progression should be reported as a CTCAE Grade 5 SAE. All worsening and/or progression of the lymphoma data will be captured as efficacy assessment data.

Hospitalization due solely to the progression of underlying lymphoma should not be reported as a serious adverse event. Clinical symptoms of progression may be reported as AEs if the symptom

cannot be determined as exclusively due to the progression of the underlying malignancy, or does not fit the expected pattern of progression for the disease under study.

Symptomatic deterioration may occur in some patients. In this situation, progression is evident in the patient's clinical symptoms, but is not supported by the tumor measurements. Alternatively, the disease progression is so evident that the investigator may elect not to perform additional disease assessments. In such cases, the determination of clinical progression is based on symptomatic deterioration. These determinations should be a rare exception, as every effort should be made to document the objective progression of underlying malignancy.

If there is any uncertainty about an AE being related only to the disease under study, it should be reported as an AE or SAE.

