7.3.2.2 Adverse Events

All AEs will be coded using the Medical Dictionary for Regulatory Activities (MedDRA) and the corresponding intensity will be graded according to NCI CTCAE v.5.0. Analysis of AEs will be performed for TEAEs, which are defined as AEs that onset or worsen in severity on or after the first dose of HMPL-689. All TEAEs will be summarized in frequency and percentage of patients for each dose level.

The same analysis will be performed for SAEs, study drug-related TEAEs assessed by the investigators, TEAEs leading to dose adjustment, or treatment discontinuation, and AEs of special interest.

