7.3. LAST KNOWN ALIVE DATE

For patients in FAS who are alive at the analysis cut-off date, the last known alive date will be derived based on the last date of the following recorded dates:

- All assessment / scan / sample collection dates (e.g. laboratory evaluation, vital sign assessment, physical examination, ECG, ECOG assessment, scan dates for tumor evaluation, etc.);
- Medication dates, including study drug, concomitant medications;
- Procedure dates;
- Date of subsequent anti-tumor therapy, including subsequent chemotherapy and oncology medication, surgery/procedure and radiotherapy;
- Adverse events start and end dates, date of change of CTCAE grade, SAE started date.

For subjects who are confirmed dead in the study, the last known alive date will also be derived according to the above rules, but this date will only be used as an alternative date to impute date of death if date of death is missing.

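### SAP 17.2 classes adverse events as treatment-emergent by onset date alone and omits the protocol's second route, worsening after the first dose

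*SAP*

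**What the plan says.** Protocol 7.3.2.2 bases the adverse event analysis on "TEAEs, which are defined as AEs that onset or worsen in severity on or after the first dose of HMPL-689". There are two routes in: a new event, or an existing event that becomes more severe.

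SAP 17.2 keeps only the first. It states "Treatment-emergent adverse events (TEAEs) are defined as AEs with onset date on or after the first dose of study medication", up to 30 days after the last dose or the start of new antineoplastic therapy, and makes an exception for late drug-related SAEs. It then lists every AE but tabulates TEAEs alone.

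The recording rules that bear on this are:

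- Protocol 6.2.5: between consent and first dose, only SAEs are collected.
- Protocol 6.3.1.3: a persistent AE is entered once, but if its severity changes "it should also be recorded on the Adverse Event CRF as a new entry". The onset date for that entry is not specified.
- Protocol 6.3.1.8: a preexisting condition becomes an AE only if it worsens during the study. Again the onset date is not specified.
- SAP 7.3 names "date of change of CTCAE grade" alongside AE start and end dates, as a separate item. SAP 7.10 uses it when checking imputed start dates, and the AE listing in SAP 17.2 shows grade changes. The TEAE rule does not use it.

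**The concern.** TEAEs are the named component of the Stage 2 primary endpoint and one component of the Stage 1 primary safety endpoint (Table 1 in both documents). The protocol's definition should reach the tables intact, or the SAP should say that it has been narrowed and why. The SAP sections supplied contain no such statement.

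The narrowing also sits badly with SAP 7.4, which takes the highest CTCAE grade in the on-treatment period as the worst post-baseline value. Worsening on drug is evidently meant to count. The onset-only rule stops some of it before the grade is looked at.

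At stake is a small, one-directional undercount of on-drug worsening, and a classification that can depend on how a site entered the event.

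**Working it through.** No figure in the plan is in question, so the check applies both definitions to each way an event can be recorded. All cases assume a complete onset date and worsening within the SAP's upper time limit.

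| Event and how it is recorded | Protocol 7.3.2.2 | SAP 17.2 |
|---|---|---|
| Starts after first dose, worsens or not | TEAE | TEAE |
| Pre-dose SAE, does not worsen | not a TEAE | not a TEAE |
| Pre-dose SAE worsens on drug; new entry dated at the worsening | TEAE | TEAE |
| Pre-dose SAE worsens on drug; new entry repeats the original onset | TEAE | not a TEAE |
| Pre-dose SAE worsens on drug; one record with a grade-change date | TEAE | not a TEAE |
| Baseline condition worsens on drug; entered with the date of worsening | TEAE | TEAE |
| Baseline condition worsens on drug; entered with its original onset | TEAE | not a TEAE |

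The definitions part in three of the seven rows. In each, the record carries a pre-dose onset date and the worsening is visible only through the grade or the grade-change date.

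The SAP's defaults do not recover these rows. SAP 7.10 presumes an event treatment-emergent when its onset date is missing or partial, and SAP 17.2 does so when classification is impossible. A complete pre-dose date is neither.

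**Size.** The documents give no number of such events. The Amendment 5 summary in the protocol puts expected enrollment at about 100.

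- Effect of one patient on a row with that denominator: 1/100 = 1 percentage point. This is a maximum, because the tables count patients, and a patient with another qualifying TEAE in the row is still counted.
- Illustration with an assumed 30 of 100 patients in some TEAE row under the protocol definition: 30.0% (exact 95% CI 21.2 to 40.0). Losing one gives 29.0% (20.4 to 38.9). Losing two gives 28.0% (19.5 to 37.9).
- SAP section 8 reports Stage 1 by dose level and Stage 2 by malignancy type, so single columns are smaller. In an assumed column of 20, one patient is 1/20 = 5 points. At the minimum dose-level cohort of 3, one patient is 1/3 = 33 points.

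The shift in the overall rates is well inside sampling error. The case for correction is fidelity to the protocol's definition.

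**The case against.** The strongest reply is that the recording rules already do most of the work. Only SAEs exist before dosing. A preexisting condition enters the AE data because it worsened, so the AE can be read as the worsening itself. A more severe persistent event gets its own entry. The exclusion criteria also remove patients with clinically significant active infection and those with unresolved prior-therapy toxicity above Grade 1 (alopecia excepted). If every site dates the new entry at the worsening, the SAP rule gives the protocol's answer.

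This stands as a limit on size, but it does not close the gap. No passage says which onset date a worsened entry carries. The SAP treats the grade-change date as a field apart from the start date. CRF version 6, on which the SAP is based, is not available to settle how the two are used together.

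A reader might go further on two points, and the documents support neither.

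- *That such an event could not be a DLT*, because SAP 17.1 defines DLTs as TEAEs. SAP 17.1 takes DLTs from a dedicated CRF page, and protocol 6.5 has the investigator confirm them within 2 business days. The TEAE wording removes nothing from that page. A complication of a screening procedure would in most cases be excluded from DLTs anyway, as having an extraneous cause.
- *That deaths from lymphoma progression wrongly inflate the fatal, serious and Grade 3 or higher counts.* Protocol 6.3.1.9 says that when progression directly causes death "the disease progression should be reported as a CTCAE Grade 5 SAE", and 6.3.1.7 also makes it an SAE, so the SAP counts what the protocol requires to be recorded. SAP 17.2 tabulates fatal, serious and Grade 3 or higher TEAEs by preferred term, with Grades 3, 4 and 5 separated and drug-related events shown on their own. AEs leading to death are listed, and SAP 17.3 lists deaths with on-treatment deaths flagged. A further row excluding progression would be a choice of presentation. The documents give no count from which to size an effect.

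**Conclusion.** The SAP's TEAE definition is narrower than the protocol's and should be aligned with it. An AE recorded with a known pre-dose onset that worsens on drug is a TEAE under protocol 7.3.2.2 and is left out of the SAP's safety tables, unless the site makes a new entry dated at the worsening.

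The effect is likely to be small: few patients, and at most 1 percentage point per patient in a row of about 100. This rests on two assumptions: that pre-dose collection is in practice confined to SAEs, as protocol 6.2.5 says, and that most worsened events are entered with the date of worsening. If sites usually keep the original onset date, more events would be lost, but still only among those that began before the first dose. DLT capture is not affected.

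**What to change.** In SAP 17.2, define TEAEs as AEs that start, or worsen in CTCAE grade, on or after the first dose, keeping the present 30-day or new-therapy limit and the exception for late related SAEs. For a worsened event, use the grade-change date as its onset.

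Three details make this workable:

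- Count only an increase above the last grade before the first dose, since protocol 6.3.1.3 covers changes in both directions.
- State how a partial grade-change date is handled; SAP 7.10 has no imputation rule for it.
- Add a line to the CRF completion guidance saying which onset date a worsened event or preexisting condition carries.

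The cost is a short SAP edit and a small change to the TEAE derivation. The SAP already treats the grade-change date as available, so no new data collection should be needed. Patients would not be double-counted, because the tables already take the worst grade once per patient and term.

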7.10. MISSING DATA

In general, all available data will be included in the analyses. Unless otherwise specified there will be no substitution of missing data, i.e. missing data will not be replaced but will be handled as 'missing' in the statistical evaluation. Partial dates may be imputed for statistical analyses for specific outcomes. In such cases, the specific imputation rules are provided below. However, as a global convention, imputed dates should not be shown in listings.

Adverse Events

If the adverse event onset date is missing or partial, the date will be compared as far as possible with the date of first dose of study medication. Adverse events will be assumed to be treatment-emergent, unless there is clear evidence (through comparison of partial dates) to suggest that the adverse event stopped prior to the first dose of study medication or started more than 30 days after last dose of study medication or new antineoplastic therapy.

Missing or partial start dates:

- If the date has no missing year and month but the day is missing:
 - If the year and month of first dose date are the same as the year and month of the start date, then the date of first dose will be used.
 - Otherwise, 1st day of the month will be used.
- If the date has no missing year, but has missing month, and the year of first dose date
 is the same as the year of the start date, the date of first dose will be used.
- If the date has no missing year, but has missing month, and the year of first dose is not the same as the year of the start date, then January 1st will be used.
- If the start date is completely unknown, then use the date of first dose.

Missing or partial stop dates:

- If the date has no missing year and month but the day is missing, then use the last day of the month.
- If the date has no missing year, but has missing month, then use December 31st of that year.
- If the stop date is completely unknown, do not impute the stop date.

Note: If the imputed stop date is earlier than the start date, then the stop date is imputed with the start date. If the imputed start date is after non-imputed end date / SAE start date / date of change CTCAE grade then set start date to end date / SAE start date / date of

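### AESI duration is calculated for ended events only, so unresolved events drop out and the reported duration is biased short

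*SAP*

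**What the plan says.** SAP 17.2 (AESI Summary) defines five AESI categories by standardised MedDRA queries: hepatic disorders, infective pneumonia, noninfectious diarrhoea, interstitial lung disease and severe cutaneous reactions. A set of count items follows, introduced by "The followings will also be summarized for each AESI category". Onset and duration are not among those items. They come in the next sentence: "Moreover, time to AESI onset (days), AESI duration (days) and AESI outcome (the number and percent of patients) will be summarized descriptively".

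The duration rule is "AESI duration (days) will only be calculated for ended AESI as (AE end date-AE start date+1". SAP 7.10 adds, for adverse events, "If the stop date is completely unknown, do not impute the stop date". An event with no end date therefore has no duration. It remains visible elsewhere: "If the AE is ongoing at the data cut-off date, it will be reported as 'Ongoing' in the listing".

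Time to onset runs from first dose to "the earliest onset date among all AESIs", with the explanation that "if a subject has multiple AESI occurrences, the earliest AESI onset date will be used as the onset date".

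**The concern.** Whether an event supplies a duration depends on how long it lasts. If follow-up is unrelated to duration, the events seen to end are a selection of the shorter ones. Events ongoing at cut-off or last contact are right-censored, and the rule removes them instead of using the time already observed. This is a stated calculation rule that gives a biased figure, not a missing detail.

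What is at stake is the description of how long the main class toxicities last, in a trial whose expansion-stage primary objective is safety and tolerability. Someone reading the AESI table would take the median as the typical time to resolution. For slow-resolving events it could be well below that.

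The onset definition raises a smaller question. Read as written, a patient with early diarrhoea and later pneumonitis contributes no pneumonitis onset.

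**Working it through.** **No plan figure to reproduce.** Neither document states an expected AESI duration, a proportion ongoing or a precision target. The direction follows from the rule. The size can only be illustrated, and every duration and follow-up window below is an assumption.

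**Inputs taken from the documents**
- Ended-only rule and descriptive summary: SAP 17.2.
- 30 days: the safety follow-up after last dose (Protocol 4.1.6). It serves as a short window, for an event starting at last dose and not followed further.
- 548 days: 18 months × 30.4375 = 547.9, from the end-of-study definition (Protocol 4.4). It serves as a long window.

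**Step 1. Fixed window W after onset, exponential durations with true median m.** Let λ = ln 2 / m.
- Share of events dropped = exp(−λW).
- Ended-only median = −ln(1 − 0.5 × [1 − exp(−λW)]) / λ.

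Example: m = 30, W = 30. Then λ = 0.0231 and exp(−λW) = 0.50, so half the events are dropped. The ended-only median is −ln(0.75) / 0.0231 = 12.5 days.

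| True median (days) | W (days) | Dropped | Ended-only median | Shortfall |
|---|---|---|---|---|
| 14 | 30 | 23% | 9.9 | 29% |
| 30 | 30 | 50% | 12.5 | 58% |
| 60 | 30 | 71% | 13.7 | 77% |
| 60 | 548 | 0.2% | 59.8 | 0.3% |
| 120 | 548 | 4% | 112.8 | 6% |

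Shortfall = 1 − ended-only median / true median.

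**Step 2. Staggered follow-up.** This is a simulation of 400,000 events with exponential durations and independent follow-up, uniform from 0 to the stated maximum.

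| True median | Maximum follow-up | Dropped | Ended-only median | Shortfall | Kaplan-Meier median |
|---|---|---|---|---|---|
| 14 | 180 | 11% | 12.4 | 11% | 14.0 |
| 30 | 180 | 24% | 22.5 | 25% | 30.0 |
| 60 | 180 | 42% | 33.0 | 45% | 60.0 |
| 120 | 180 | 62% | 41.5 | 65% | 119.8 |
| 14 | 548 | 4% | 13.5 | 4% | 14.0 |
| 30 | 548 | 8% | 27.6 | 8% | 30.0 |
| 60 | 548 | 16% | 50.2 | 16% | 60.0 |
| 120 | 548 | 30% | 81.3 | 32% | 119.8 |

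Kaplan-Meier recovers the true median wherever it is reached. Where follow-up is too short (true median 60 with a fixed 30 days, for instance), it reports the median as not reached. Ended-only gives 13.7 days there.

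**Step 3. Which events are dropped.** Across the staggered scenarios run (maximum follow-up 60 to 548 days), 15% to 41% of dropped events had a true duration below the true median, because short events with late onset are dropped too.

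**Step 4. Onset.** With assumed category incidences of 20, 10, 30, 5 and 3% and onset medians of 45, 120, 90, 150 and 30 days, the pooled first-onset median is about 60 days. That one figure stands for category medians of 30 to 150 days, and 15% to 36% of the onsets within a category are never used.

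**The case against.** **Unresolved events are not hidden.** The rule says openly that it covers ended events. AESI outcome is tabulated by number and percent, and ongoing events are marked in the listing. This stands, and it limits the harm. But the tables show only that unresolved events exist; they do not correct the duration.

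**The figure carries little weight.** AESI duration is not a named endpoint in Protocol Table 1, and no visible test or stopping rule uses it. This stands.

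**The rule does not remove the longest events.** A reader might infer that it does. A very long event that has resolved is kept, and a short late-onset event is dropped (Step 3). The supportable statement is that unresolved events are dropped and that these tend to be longer.

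**Amendment 5 is not shown to worsen the problem.** Protocol 5.7.13 and 5.8.2 say that patients who stop drug for reasons other than progression now also leave the study, so a reader might expect more unresolved AESIs. But Protocol 5.8.1 still brings early leavers back at 30 ± 7 days and follows ongoing related events, and Protocol 6.6 follows all unresolved events to resolution, stability or another stated end. Neither passage was shortened. Protocol 4.1.6 is narrower: after the safety period, only unresolved related serious events are reported. Sections 4.1.6 and 6.6 need reconciling, but that difference does not depend on the amendment.

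**Onset by category may be intended.** The onset sentence directly follows a per-category list, and the remark on multiple occurrences would also fit first onset within a category. First onset of any AESI is also a legitimate statistic. The wording is therefore ambiguous, not shown to be wrong.

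**Plain Kaplan-Meier on AE records is not enough.** Protocol 6.3.1.3 opens a new CRF entry when a persistent event changes grade, so one episode can become several short records. Death is not ordinary censoring. With about 100 patients (Protocol amendment summary) across five categories, some medians will not be estimable. All of this stands and shapes the fix.

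**Conclusion.** The point holds, as a minor one. Calculating duration only for ended AESIs biases the descriptive summary short whenever follow-up is unrelated to duration. Nothing else in the SAP corrects it.

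The documents do not support a single percentage for the understatement. Under exponential durations and the assumed windows, it runs from negligible (short events, long follow-up) to more than half (slow-resolving events, short follow-up). The direction does not depend on the exponential form; the size does, and so does the agreement of Kaplan-Meier with the true median on independent censoring.

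AESI incidence, grade, seriousness, discontinuation and outcome counts are unaffected. The onset definition needs clarifying and is not in itself an error.

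**What to change.** Amend SAP 17.2 as follows.

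1. Summarise AESI duration by Kaplan-Meier, with ongoing events censored at last AE follow-up or data cut-off. Show fatal events separately or treat death as a competing outcome.
2. Report the number of events ongoing beside the median and its 95% CI.
3. Define the unit as the episode, joining CRF records that differ only because the grade changed. State how repeat episodes in one patient are handled, since the usual interval treats them as independent.
4. Present duration by AESI category. Where a category is sparse, give ended-event durations plus the number ongoing.
5. State that time to onset is the first onset within each AESI category. A first-onset-of-any-AESI figure can be kept alongside if wanted, labelled as such.

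The cost is a few lines of SAP text and a small amount of programming. The SAP already plans Kaplan-Meier for PFS and DoR (16.5, 16.6), so no new method is needed. The downside is wide or non-estimable intervals in small categories.
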